10.1.3 Adverse event report items

For adverse events that develop, the following information will be reported on a CRF:

- 1) Name of adverse event
- 2) Severity (CTCAE grade 0–5 and serious/nonserious)
- 3) Causal relationship with the treatment protocol
- 4) Onset date, date of outcome confirmation, and outcome
- 5) Presence or absence of treatment

*Investigator will assess if the AE is related to study procedure, regorafenib, or nivolumab, if possible

10.1.4 Determination of a causal relationship

A causal relationship with the treatment protocol is determined according to the following step:

Causal relationship

The assessment of the causal relationship between an AE and the administration of treatment

is a clinical decision based on all available information at the time of the completion of the

CRF.

The assessment is based on the question whether there was a "reasonable causal relationship" to the study treatment in question.

Possible answers are "yes" or "no"

An assessment of "no" would include:

1. The existence of a clear alternative explanation, e.g. mechanical bleeding at surgical site.

or

2. Non-plausibility, e.g., the subject is struck by an automobile when there is no indication that the drug caused disorientation that may have caused the event; cancer developing a few days after the first drug administration.

An assessment of "yes" indicates that there is a reasonable suspicion that the AE is associated with the use of the study treatment.

| Classification | | Definition |
|----------------|------------------|---|
| Definite | Definite | A causal relationship with the treatment protocol is plausible, |
| (certain) | | and symptoms cannot be explained by an exacerbation of the |
| | | underlying disease, complications, or other drugs/treatments |
| Probable | Probable, likely | A causal relationship with the treatment protocol is |
| (likely) | | reasonable, and symptoms are unlikely attributable to the |
| | | exacerbation of the underlying disease, complications, or other |
| | | drugs/treatments |
| Possible | Possible | A causal relationship with the treatment protocol is |
| | | reasonable, and symptoms can be explained even with an |
| | | exacerbation of the underlying disease, complications, or other |
| | | drugs/treatments |
| Unlikely | Unlikely | A causal relationship with the treatment protocol is |
| | | improbable, and symptoms can be explained by exacerbation |
| | | of the underlying disease, complications, or other |
| | | drugs/treatments |
| Not related | Unrelated | There is no causal relationship with the treatment protocol, |
| (unrelated) | | and symptoms can be clearly explained by an exacerbation of |
| | | the underlying disease, complications, or other |
| | | drugs/treatments |
| Unassessable | Unassessable | There is insufficient data to determine a causal relationship, |
| (conditional) | | and more detailed data is required (conditional), or evaluation |

Table 11: Classification of causal relationships

| | is difficult |
|--|--------------|
| | |

10.1.5 Follow-up observation upon the onset of an adverse event

When adverse events develop, the attending physician will immediately take appropriate measures.

Follow-up observation will be performed even after completion of the adverse event evaluation period (refer to section 11.1.6) until recovery from or alleviation of the symptoms is confirmed (test values). However, when one or more of the following conditions apply, follow-up observation of adverse events can be concluded.

*Follow-up of adverse events shall be concluded when:

- It is deemed that the adverse event is not serious, a causal relationship can be ruled out, and at least 30 days have passed since the day of the last dose
- The principal investigator has judged that symptoms are stable and that there is no major medical problem
- Aftertreatment has been administered and a causal relationship with the investigational drug cannot be evaluated
- Follow-up observation is difficult because the subject has been transferred to another hospital or for another reason
- · The subject refuses follow-up observation
- Death

10.1.6 Adverse event evaluation period

In the present trial, the adverse event evaluation period will last from "the treatment start date" until "30 days after the day of the final investigational drug doses, or before the start of aftertreatment if that occurs beforehand, whichever is earliest." Data pertaining to any adverse events that occur during this period will be collected.

Data will also be collected regarding adverse events from 31 days after the day of the final investigational drug doses when it is deemed that there is a causal relationship with the treatment protocol.

After PD is confirmed, new adverse events that occur as a result of disease progression will not be included.

10.2 Reporting of serious adverse events

10.2.1 Definition of serious adverse events

Of the adverse events described in section "11.1 Adverse event evaluation," those that meet any of

the following will be defined as "serious adverse events."
- 1) Adverse events that cause death or are life-threatening
- 2) Adverse events that cause permanent or marked impairment/dysfunction
- 3) Adverse events that cause congenital abnormalities/birth defects
- 4) Adverse events that require hospitalization or prolongation of the hospital stay

However, the following will be exempt:

- -Hospitalization or death due to the underlying disease after PD is confirmed
- -Hospitalization or prolongation of the hospital stay that was planned beforehand
- -Hospitalization or prolongation of the hospital stay unrelated to adverse events
- -Hospitalization or prolongation of the hospital stay of <24 h for follow-up observation only

5) Medically important events are defined as events that endanger the subject or events that require internal medicine or surgical treatment to prevent the abovementioned outcomes.

10.2.2 Mandatory reporting and reporting procedures for the principal investigator (or subinvestigator)

1) Reporting to the director of medical institution implementing the trial and the trial coordinating committee

(1) Initial report

In the event of a serious adverse event (refer to section "11.2.1 Serious adverse events"), the trial principal investigator (or subinvestigator) is to immediately take appropriate action. The subinvestigator will report promptly to the principal investigator.

The principal investigator (or subinvestigator) will report the occurrence of serious adverse events to the directors of the medical institutions implementing the trial and trial coordinating committee in writing (by e-mail or fax) or verbally (by telephone) within 24 h of discovery of the adverse event concerned. When the initial report is made without using the "Report form for serious adverse events," a written report is to be submitted in a promptly (by e-mail or fax).

Furthermore, the details of serious adverse events will be reported to the directors of the medical institutions implementing the trial and the trial coordinating committee within 5 working days of discovering the adverse event.

*Reporting by e-mail is recommended.

② Additional reports

The principal investigator (or subinvestigator) will follow-up serious adverse events (refer to section "11.1.5 Follow-up upon adverse event onset"). Additional information will be recorded on the "Report form for severe adverse events" (additional report), and sent to the directors of the medical institutions implementing the trial and the trial coordinating committee.

Trial coordinating committee contact details: Office of the trial coordinating

committee

E-mail: [contact] [contact] ([name]), [contact]

When the trial coordinating committee, directors of the medical institutions implementing the trial, institutional review board, or trial sponsor request further information, the principal investigator (or subinvestigator) will comply with additional reports.

10.2.3 Mandatory reporting and reporting procedures for the trial coordinating committee

With regard to serious adverse events reported in the initial and additional reports, the trial coordinating committee will judge the necessity of reporting (in accordance with "Article 80-2, paragraph 6 of the Pharmaceutical Affairs Law" and "Article 273 of the Pharmaceutical Affairs Law Enforcement Regulations") the severity, causal relationship, and predictability to the regulatory authority concerned (Pharmaceuticals and Medical Devices Agency: PMDA).

The detailed reporting procedure will be performed in accordance with the "Procedures regarding the handling of safety information."

1) Reporting to the principal investigator

According to the decision noted above, reported serious adverse events will be reported by the trial coordinating committee to each principal investigator without delay. Each principal investigator will report to the director of the medical institution concerned as quickly as possible in accordance with the regulations of each medical institution.

2) Reporting to the PMDA

When reporting to the PMDA is deemed necessary, the trial coordinating committee will comply in accordance with article 273 of the Pharmaceutical Affairs Law Enforcement Regulations and other related notifications.

3) Reporting to the Data and Safety Monitoring Committee

When the review of serious adverse events by the Data and Safety Monitoring Committee is deemed necessary, the trial coordinating committee will submit a written report requesting the opinion of the committee with regard to the assessment of the principal investigator and trial coordinating committee regarding the adverse event concerned, as well as the validity of the response to the adverse event concerned (judgments of the severity of the adverse event, causal relationship, and predictability).

4) Reporting to the investigational drug supplier/concomitant drug supplier

As a general rule, serious adverse events reported by the principal investigator(or subinvestigator) will be reported by the trial coordinating committee to the investigational drug

supplier (i.e., Ono Pharmaceutical) within 24 h.

10.2.4 Duties of the Data and Safety Monitoring Committee

The Data and Safety Monitoring Committee will examine the details of adverse event reports, and submit written advice to the trial coordinating committee with regard to countermeasures such as continuation of the trial and the need for protocol revision. Procedures will follow the prescribed "Procedures for the Data and Safety Monitoring Committee" attached separately.

10.3 Collection of safety information

When information regarding the investigational drugs is obtained from the investigational drug supplier, the trial coordinating committee will respond in accordance with article 273 of the Pharmaceutical Affairs Law Enforcement Regulations and other related notifications. The trial coordinating committee will report the safety information concerned to each principal investigator and each principal investigator will report to the director of their medical institution as promptly as possible in accordance with the regulations of each medical institution.

The detailed reporting procedures will follow the "Procedures for handling safety information." In addition, the need for revision of the protocol and informed consent form, as well as the need to provide an explanation to subjects will be judged, and if deemed necessary, such needs will be addressed.

10.4 Pregnancy

During individual trial participation periods and during periods of contraception, when information regarding pregnancy is obtained from a subject, administration of the investigational drug will be terminated, and the information will be reported using the designated form without delay to the trial coordinating committee (as a general rule, within 24 h of obtaining the information). As a rule, the trial coordinating committee will submit the form obtained to the investigational drug suppler (Ono Pharmaceutical) within 24 h. The principal investigator (or subinvestigator) will conduct a follow-up survey regarding the pregnancy of the subject concerned, and report this in writing. The reporting procedures will follow the prescribed "Procedures for handling safety information" attached separately.

10.5 Overdosing

In the dose escalation cohort, overdosing is given when the dose exceeded the dose prescribed at each level shown in Table 6.1.1a, and Expansion cohort exceeds the RD determined based on the result of dose escalation cohort.

In the event of an overdose of the investigational drug, the principal investigator (or subinvestigator) will take the appropriate countermeasures, and report these using the designated

form without delay to the trial coordinating committee (as a general rule, within 24 h of obtaining the information). As a rule, the trial coordinating committee will submit the form obtained to the investigational drug suppler (Ono Pharmaceutical) within 24 h. The reporting procedures will follow the prescribed "Procedures for handling safety information" attached separately

11 Response evaluation and endpoints

11.1 Response evaluation

The tumor response evaluation will be conducted in accordance with the RECIST guideline version 1.1 and irRECIST (Appendices 2 and 3). Thoracoabdominal and pelvic contrast-enhanced CT or MRI will be performed (if the patient is allergic to the contrast medium, plain scans are permitted), and the tumor response will be according to image measurements. In the event of PD of the primary disease, refer to section "8.5 Tumor assessment."

Furthermore, the period of 4 weeks (28 days) to determine the best overall response of CR or PR is not required in this study.

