2.8.2 Planned number of enrollments

Dose-escalation cohort: Three to six patients per level, for a total of 9–18 patients.

Expansion cohort: Approximately 30 patients in total.

If two or more cases of CR/PR or SD \geq 4 months were observed in specific cancer types, we will consider adding around 10 patients with same cancer type in expansion cohort.

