8.5 Tumor evaluation

For all subjects, tumor evaluations will be conducted using the irRECIST and RECIST guidelines version 1.1. Tumor evaluations of the chest, abdomen, and pelvis (when deemed clinically necessary) will be conducted at each time point listed below until an exacerbation is

confirmed. Thoracoabdominal and pelvic contrast-enhanced CT or MRI will be performed (if the subject is allergic to the contrast medium, plain scans are permitted).

- Less than 21 days before enrollment in this trial
 - Evaluations will be performed in weeks 6, 12, 18, and 24 after the beginning of treatment (followed by every 9 weeks until week 42, then every 12 weeks thereafter).
- When treatment is terminated for reasons other than an exacerbation of the underlying disease on imaging, an evaluation will be performed within 2 weeks of dosing completion. Furthermore, tumor evaluations are to be conducted in accordance with the schedule until an exacerbation of the underlying disease is confirmed, or until commencement of a new anticancer treatment.

The principal investigator and radiologist will conduct tumor evaluations in accordance with the irRECIST and RECIST guidelines version 1.1 (refer to appendices 2 and 3). The decision to continue the investigational drugs will be determined on the basis of these evaluations, including the effects on target and nontarget lesions and the appearance of new lesions. When disease progression is first observed on imaging in clinically stable patients, participating medical institutions will conduct repeat scans 4 weeks after the initial identification of disease progression via an image evaluation to determine disease progression. Administration of the investigational drug can continue until the repeat scan is conducted (refer to Table 10). The criteria for clinical stability are listed below.

- Absence of clinical signs and symptoms indicating disease progression.
- No worsening of ECOG PS.
- No sudden disease progression observed

• Absence of tumor enlargement in the main anatomical site requiring new emergency medical intervention (e.g., spinal cord compression).

Furthermore, in the present trial, a maximum of 10 lesions can be included as target lesions, with a maximum of five lesions per organ.

| Table 8.5: Imaging and investigational drug dosing after disease progression is first observed |
|--|
| on imaging |

| | Clinically stable | | | | Clinically unstable | | | |

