11.2.2 Objective response rate (ORR)

ORR is defined as the proportion of patients whose best overall response, as per the RECIST guideline version 1.1 and irRECIST, is either CR or PR.

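### The only planned ORR counts CR or PR seen on a single scan; a confirmed ORR, obtainable from scans already scheduled, should be prespecified and reported beside it

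*Combined protocol and SAP*

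**What the plan says.** Section 11.1 states that "the period of 4 weeks (28 days) to determine the best overall response" is not needed for CR or PR. Section 11.2.2 then counts as a responder any patient whose best overall response, under RECIST 1.1 and irRECIST, "is either CR or PR". Section 12.7.1 gives ORR an exact binomial interval. No confirmed version is planned anywhere.

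Section 8.5 schedules scans at weeks 6, 12, 18 and 24, then every 9 weeks to week 42, then every 12 weeks. Table 8.2 allows one week either side up to week 24.

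For progression, Section 8.5 says that for clinically stable patients the sites "will conduct repeat scans 4 weeks after the initial identification of disease progression", and that "Administration of the investigational drug can continue until the repeat scan is conducted". Section 11.1 adds: "In the event of PD of the primary disease, refer to section" 8.5. The PFS definition in Section 11.2.3 counts RECIST 1.1 progression at the date of the imaging examination, and also documented clinical progression. It mentions no repeat scan.

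**The concern.** A tumour measurement carries error. When best response is the best of several readings and one is enough, a patient near the PR threshold has several chances to cross it by error, and a later reading above the threshold does not reverse the classification. With no control arm, there is no comparison in which this would cancel.

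At stake is how the activity estimate is read. Section 12.5 sets no decision rule, but says the regimen will be regarded as promising if, among other things, the secondary endpoints support efficacy. With no target ORR, the reported estimate and its interval carry that judgement, and the exact interval covers sampling error only.

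**Working it through.** **No stated figure to reproduce.** The plan gives no target ORR, null rate, power or measurement-error rate.

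**Can the scheduled scans confirm a response?** With the one-week window, consecutive scans from week 6 to week 24 are at least (12 − 1) − (6 + 1) = 4 weeks and at most (12 + 1) − (6 − 1) = 8 weeks apart. Later nominal gaps are 9 weeks (24 to 33 to 42) and then 12 weeks. Any response followed by another scheduled scan therefore has a reading at least 4 weeks later, with no added imaging.

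**Direction.** Every confirmed responder is also an unconfirmed responder on the same scans. So unconfirmed ORR ≥ confirmed ORR, whatever the error rate.

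**Size, under stated assumptions.** Let p be the true response rate, f the chance that a non-responder is read as CR or PR at one scan, and k the number of scans.

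- p = 10% to 40%: the single-agent checkpoint-inhibitor range quoted in Section 2.4.1, used for illustration.
- f = 1% to 5% and k = 1 to 4: assumptions, with errors independent between scans.
- n = 30: approximate expansion cohort size, Section 12.8.

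Unconfirmed ORR = p + (1 − p)[1 − (1 − f)^k].

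Confirmed ORR = p + (1 − p)·R, where R is the chance of two consecutive false readings in k + 1 scans (the extra scan can confirm the last), with no true response lost.

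Middle case, p = 0.20, f = 0.02, k = 4:
- Unconfirmed: 0.20 + 0.80 × (1 − 0.98^4) = 0.20 + 0.80 × 0.0776 = 0.262.
- R = 1 − [0.98^5 + 5(0.02)(0.98^4) + 6(0.02²)(0.98³) + (0.02³)(0.98²)] = 0.0016, so confirmed = 0.20 + 0.80 × 0.0016 = 0.201.
- Difference: 6.1 points, or 30 × 0.061 = 1.8 patients.

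| p | f | k | Unconfirmed | Confirmed | Difference (points) | Patients of 30 |
|---|---|---|---|---|---|---|
| 40% | 1% | 1 | 40.6% | 40.0% | 0.6 | 0.2 |
| 20% | 1% | 4 | 23.2% | 20.0% | 3.1 | 0.9 |
| 20% | 2% | 4 | 26.2% | 20.1% | 6.1 | 1.8 |
| 20% | 5% | 4 | 34.8% | 20.8% | 14.1 | 4.2 |
| 10% | 5% | 4 | 26.7% | 10.9% | 15.8 | 4.7 |

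Differences are taken before rounding. The first and last rows are the extremes of the assumed range. Correlated errors, such as a baseline measured too large, would make confirmation remove less than shown.

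**Against sampling error.** The confidence level is not stated; 95% two-sided is assumed. The exact interval is 7.7% to 38.6% for 6/30 and 12.3% to 45.9% for 8/30. Two extra responses move the estimate by 2/30 = 6.7 points, well inside either interval.

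**The case against.** The waiver is explicit and prespecified. The primary aim is safety and the MTD and recommended dose by DLT. ORR is secondary, Section 12.7 allows efficacy to be shown as listings only, and Section 12.5 calls the study exploratory. DCR does not change if an unconfirmed PR is reclassified as SD. The likely shift lies within sampling error. Section 12.12.2 lists tumour assessments by patient, and Section 12.4.2 allows additional analyses. Version 1.7 is dated April 2020 and enrolment was planned for January to October 2018, so replacing the main definition now could be post hoc. Confirmation also loses some true responses.

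Most of this stands, and it argues against replacing the ORR rather than against adding a second figure. The exact interval does not cover a shift in one direction. Patient listings are not a prespecified estimate, and Section 12.4.2 would have a confirmed ORR reported as unplanned.

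Three stronger readings are tempting, and the documents do not support them.

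- *That measurement noise is filtered out of progression but counted as response.* The repeat scan in Section 8.5 and Table 8.5 is written as a rule for continuing treatment. Section 11.2.3 counts unconfirmed progression for PFS, so a single noisy reading can be an event there too. For best overall response the position is unclear: Section 11.1 points to 8.5 without saying what the repeat scan changes, and the RECIST and irRECIST appendices are not in the text available.
- *That a particular share of the reported responses would be noise.* Any such share rests on measurement error, depth of response and regrowth, none of which the documents give.
- *That noise would drive enrolment under Section 2.8.2.* For an assumed 10 patients of one type and a 5% true rate, P(two or more CR/PR) rises from 8.6% to 21.8% if 4% of non-responders are misread at some scan (0.05 + 0.95 × 0.04 = 0.088). But the trigger begins "If two or more cases of CR/PR or SD" and also accepts stable disease of at least 4 months, through which many misread patients could qualify anyway. It only leads the team to consider adding patients.

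**Conclusion.** The point holds as a reporting gap of minor to moderate weight. The only planned ORR is unconfirmed and cannot be lower than the confirmed ORR from the same scans. That direction needs no assumption. The size, about 0.6 to 16 percentage points, depends wholly on the assumed false-response rate, number of scans, true rate and independence of errors, so no single figure can be claimed. No formal decision changes, because ORR has no threshold; what changes is how firmly activity can be described. The documents show an asymmetry between response and progression for treatment continuation, but not for PFS, and for best overall response the text needs clarifying.

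**What to change.** - **11.2.2 and 12.7.1:** label the existing ORR unconfirmed. Prespecify a confirmed ORR, meaning CR or PR criteria still met at a scan at least 4 weeks later, using the scheduled scans. Report it with its exact interval next to the unconfirmed figure.
- **12.5:** base any statement about activity on both figures.
- **11.1 and 8.5:** state whether best overall response uses first or confirmed progression, so that the cross-reference has one meaning. This concerns the endpoint only.
- Record the addition and its timing in the clinical study report, as Section 12 already requires for changes to the analysis plan.

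The cost is wording and one derived variable, with no extra scans. The downside is a confirmed figure that is usually lower and misses some true responders: those whose first response is at their last scan, and those whose confirming scan reads just above the threshold. Showing both figures makes that visible.
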